## **STUDY DESIGN**

**Inclusion Criteria:** We request permission to study up to 12 subjects so that we will have 10 evaluable subjects with complete sampling at all time periods.

1. Male or female  $\geq 18$  and  $\leq 60$  years of age, Body Mass Index (BMI)  $<40$ .
2. Generally in good health as determined by the Principal Investigator based on prior medical history, American Society of Anesthesiologists physical status I or II
3. Normal blood pressure (systolic 90-140 mmHg; diastolic 50-90 mmHg) resting heart rate 45-100 beats per minute) without medication
4. Female subjects of child-bearing potential and those  $< 1$  year post-menopausal, must be practicing highly effective methods of birth control such as hormonal methods (e.g., combined oral, implantable, injectable, or transdermal contraceptives), double barrier methods (e.g., condoms, sponge, diaphragm, or vaginal ring plus spermicidal

jellies or cream), or total abstinence from heterosexual intercourse for a minimum of 1 full cycle before study drug administration.

Exclusion Criteria:

1. Hypersensitivity, allergy, or significant reaction to any ingredient of Pitocin®
2. Any disease, diagnosis, or condition (medical or surgical) that, in the opinion of the Principal Investigator, would place the subject at increased risk (active gynecologic disease in which increased tone would be detrimental e.g., uterine fibroids with ongoing bleeding), compromise the subject's compliance with study procedures, or compromise the quality of the data
3. Women who are pregnant (positive result for serum pregnancy test at screening visit), women who are currently nursing or lactating, women that have been pregnant within 2 years
4. Subjects with neuropathy, chronic pain, diabetes mellitus, or taking benzodiazepines or pain medications on a daily basis.

**Study Visit 1:** The participant will report to the Clinical Research Unit (CRU) or Piedmont Plaza II at least 1 day prior to study visit 2. The participant will review and sign the Informed Consent. After informed consent is adequately obtained, a detailed medical history will be obtained from the participant, female participants will have a urine sampled tested to determine pregnancy status. The research nurse will train the participants to estimate pain quantitatively using a 2 cm^2 Peltier controlled thermode (TSA®) applied to a forearm with 5 sec presentation of stimuli at 39, 41, 43, 45, 47, 49, and 50°C, using a 11 point numerical verbal scale (NRS) anchored at 0 for no pain and 10 for the worst pain imaginable. Typically, the participant is exposed to temperatures between 38° and 51° C using a random staircase method. After this training, we will ask them to report pain intensity on the 0-10 NRS scale every minute for 5 minutes upon exposure to a 4 cm^2 Peltier controlled thermode at 45°C. Finally, they will place first the fingertips of their hand and then the volar wrist, on a device and report when they first perceive a sensation as the surface vibration frequency declines from 1 kHz to 1 Hz. We have found this training session significantly reduces anxiety and variability in pain and hypersensitivity ratings on subsequent study days.

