## Protocol

### Pharmacokinetics of intravenous oxytocin and effects on sensory function in healthy volunteers

**PRIMARY GOAL:** Measure oxytocin in plasma after brief intravenous infusion and model its pharmacokinetics.

**METHODS:** Equal numbers of healthy adult men and women will be recruited (ten total). At least 1 day prior to study subjects will be trained to rate pain in response to heat applied to the lateral calf using a Peltier controlled thermode and to indicate when they first perceive a vibratory stimulus on the fingertips and wrist.

Subjects will return for study visit two in which an intravenous catheter will be inserted in the arm and, after baseline measures of response to heat and determination of vibration frequency threshold, subjects will receive oxytocin (Pitocin®), 10 IU over 10 minutes. Venous blood samples (5 ml) will be obtained before and at 2, 5, 10, 15, 30, 45, 60, 90, 120, 180, and 240 minutes after the end of the oxytocin administration by removal of blood from the intravenous catheter.

We will abandon an individual participant's study and schedule another participant should we be unable to successfully place the intravenous catheter.

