## **Study Visit 2**

On the second visit, the participant will report to the CRU, in the morning after having had nothing to eat or drink since midnight. A peripheral intravenous catheter will be inserted into a vein in an upper extremity and lactated Ringers solution infused at 1.5 ml/kg/hr for the duration of the study. After obtaining baseline measures (random presentation of 5 sec heat stimuli between 39 and 50°C, 5 minute presentation of a 45°C stimulus, and vibration frequency perception threshold as described in Visit 1), oxytocin (Pitocin®, 10 IU) will be administered intravenously over 10 minutes.

Venous blood will be sampled (5 ml) before the infusion and at 2, 5, 10, 15, 30, 45, 60, 90, 120, 180, and 240 minutes after oxytocin injection via the indwelling intravenous catheter. We will also repeat vibration frequency perception threshold in fingertips and wrist between the samples after samples at 5, 20, 45, 60, 120, and 180 minutes. In addition, we will ask them to rate pain intensity every minute for 5 minutes with a 45° stimulus after samples at 30, 60, 120, and 180 minutes (adjacent figure) and rate pain intensity to single, 5 second duration stimuli from 39°C to 50°C after samples at 60, 120, and 180 minutes as on the first visit.

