## **STATISTICAL RATIONALE**

**Primary outcome measure** is the concentration of oxytocin in plasma at defined times after intravenous infusion. We request a convenience sample of 10 subjects for the purpose of preliminary data to provide variance estimates that will inform federal grant

submission for use of the pharmacokinetic parameters from this sample or proposal of a larger sample size to adequately characterize such parameters.

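### Does aiming for 10 subjects with all 12 blood draws complete put the pharmacokinetic analysis at risk when a dosed subject misses a draw?

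*Combined protocol and SAP*

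**What the plan says.** The target and ceiling appear once, at the head of the inclusion criteria in Study Design: "We request permission to study up to 12 subjects so that we will have 10 evaluable subjects with complete sampling at all time periods".

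The Methods paragraph of the Protocol section schedules blood samples "before and at 2, 5, 10, 15, 30, 45, 60, 90, 120, 180, and 240 minutes after the end of the oxytocin administration", taken "by removal of blood from the intravenous catheter". Study Visit 2 lists the same times and route. That is one sample before dosing and 11 after.

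One explicit rule covers abandoning a participant, also in Methods: "We will abandon an individual participant's study and schedule another participant should we be unable to successfully place the intravenous catheter". It applies before any drug is given.

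The primary goal is "Measure oxytocin in plasma after brief intravenous infusion and model its pharmacokinetics". Statistical Rationale names the plasma concentration at set times as the primary outcome and justifies the number as follows: "We request a convenience sample of 10 subjects for the purpose of preliminary data to provide variance estimates". It names no pharmacokinetic model or estimation method, no analysis set and no handling of a missed sample.

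**The concern.** If evaluable means that all 12 samples were obtained, a subject who received the full infusion and lost only the 240-minute sample would not count, although 11 of 12 concentrations are in hand. A pharmacokinetic model can be fitted with unequal numbers of samples per subject, so such a rule would be stricter than the primary goal requires.

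The allowance is also thin. Twelve subjects give 12 × 12 = 144 draws, and three missed draws in three different subjects (3/144 = 2.1%) would leave nine complete profiles. If the decision to keep or drop a partial profile were made after the concentrations were known, it could shift the variance estimates that the sample is meant to supply.

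**Working it through.** **Inputs from the protocol.** Ceiling 12 and target 10 complete (Study Design); draws per subject 1 + 11 = 12 (Methods, Study Visit 2); 10 is a convenience sample (Statistical Rationale). The ceiling of 12 cannot be re-derived because no attrition rate is given. It allows a shortfall of 2/12 = 16.7%.

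**Assumed inputs.** The rate of failed draws, f, is not in the documents. A range of 0.5% to 5% per draw is used, with all 12 subjects enrolled.

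**Step 1: chance of 10 complete profiles, independent failures.** The probability that one subject is complete is p = (1 − f)^12. The chance of reaching the target is the binomial probability P(X ≥ 10 | 12, p).

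| f | p | P(at least 10 of 12) |
|---|---|---|
| 0.5% | 0.942 | 0.971 |
| 1% | 0.886 | 0.852 |
| 2% | 0.785 | 0.505 |
| 3% | 0.694 | 0.238 |
| 5% | 0.540 | 0.037 |

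An 80% chance needs f of no more than about 1.2%.

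**Step 2: the same, with failures clustered within subjects.** All draws come through an indwelling catheter, so a failed line tends to cost one subject several samples. With a beta-binomial model and an assumed intraclass correlation of 0.3, p becomes 0.954, 0.910, 0.868 and 0.789 at f = 1%, 2%, 3% and 5%. The chance of at least 10 complete becomes 0.984, 0.913, 0.795 and 0.518. At a correlation of 0.5 it is 0.97 at f = 2% and 0.91 at f = 3%.

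**Step 3: what a shortfall costs.** The sample is there to estimate variances, so the relevant measure is the relative standard error of a standard deviation, about 1/√(2(n − 1)) under normality.

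| n | Relative SE of an SD |
|---|---|
| 8 | 1/√14 = 26.7% |
| 9 | 1/√16 = 25.0% |
| 10 | 1/√18 = 23.6% |
| 12 | 1/√22 = 21.3% |

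Falling from 10 to 9 adds 1.4 percentage points; keeping all 12 instead of 10 removes 2.3. Even at f = 2% with independent failures, where the chance of 10 complete is only 50%, the chance of at least 8 is 91%.

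**Step 4: what the wording does.** The Study Design sentence ties a request for up to 12 participants to the aim of 10 complete profiles. It does not say that incomplete profiles are set aside, and neither does any other section. The two extra places are there because some sampling may be incomplete, so replacement up to the ceiling is the natural reading. The catheter rule in Methods is a separate event before dosing and does not confine replacement to that case.

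**The case for a change.** The strongest case for a change is that this is the only place where evaluability is described, and that a sentence or two would settle the handling of partial profiles before any concentrations are seen. With at most 12 subjects, each inclusion decision carries weight. If evaluability allowed one missed draw, the chance of 10 evaluable subjects at 2% loss per draw would rise from 50% to 99.8% with independent failures, and from 91% to 98% with clustering.

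Part of this stands. The protocol is silent on the point, and the arithmetic is correct. What does not stand is the step from silence to an unsound analysis. The improved percentages measure the chance of reaching a threshold that carries no power or precision claim. Complete sampling is also a coherent target for an outcome defined as concentration at set times, since it gives 10 values at every time. Whether it is stricter than the modelling needs cannot be settled from the documents, because no model is named: a mixed-effects fit tolerates gaps readily, while separate fits to each subject depend more on well-placed samples.

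**Conclusion.** No change follows. The gap is a detail left unstated, and analysts modelling pharmacokinetics would fill it in the ordinary way: fit the available concentrations from each dosed subject at their actual times and report how many contribute at each time. Complete sampling then works as a recruitment target.

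If incomplete profiles were nevertheless dropped, ending with 9 subjects would raise the relative standard error of a standard deviation from 23.6% to 25.0%. That is small for a preliminary convenience sample meant to inform either use of its parameters or a larger study. This figure rests on the normal approximation. The chances of reaching 10 rest on assumed failure rates and on the assumed degree of clustering, so they are illustrations only. The conclusion also relies on no section ordering the exclusion of a partial profile, and none does.

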### **Safety and Monitoring:**

**Assessment of Side Effects:** Significant side effects are defined as changes > 30% from baseline in the mean arterial pressure, HR, or oxyhemoglobin pulse oximetry < 90. Any unexpected or serious side effects will be reported to the IRB within 24 hrs.

Peripheral oxyhemoglobin saturation, BP and HR will be measured non-invasively before and 15, 30, 60, 120, 180, 240, minutes after intravenous oxytocin injection. If either BP or HR change by > 30%, or oxyhemoglobin saturation decreases to less than 90, and require treatment, these vital signs will be repeated at 5-minute intervals until vital signs are stabilized.

**Treatment of Side Effects:** Mean blood pressure elevations greater than 30% of baseline will be treated with labetalol 5-15 mg IV incrementally until BP elevation is less than 30% elevated. Reductions in mean BP > 30% of baseline will be treated with incremental ephedrine 5-20 mg, IV. Heart rate (HR) reductions or elevations > 30% of

baseline will be treated with incremental glycopyrrolate 0.2 mg IV or propranolol 0.2 mg IV, respectively. Peripheral oxyhemoglobin desaturation (< 90) will be treated with supplemental oxygen, nasal cannula, face mask, or non-rebreathing mask depending upon the degree desaturation and the response to therapy.

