## **RISKS**

Risks of intravenous cannulation include pain on insertion and bruising at the site. Risks from the FDA approved heat stimulus device are pain, and the subject can stop testing at any time if the pain they perceive is such that they do not want to continue. Please note that these devices are used in many pain clinics routinely and have multiple fail-safe designs to avoid thermal burn. Risks from the non-regulatory vibratory device are related only to microshock and are addressed in the Appendix.

Risks of oxytocin are primarily restricted to uterine contraction in the presence of pregnancy, since oxytocin receptors are not present in the non-pregnant uterus (Package insert attached).

Additionally there is the possibility of a feeling of being flushed, headache and increased heart rate with no significant change in blood pressure during or immediately after the infusion. These events have been reported by previous participants but were short lived, lasting approximately 12-15 minutes.

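### Pregnancy is tested once, at Visit 1, with no maximum interval to dosing and no re-check at Visit 2 before oxytocin

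*Combined protocol and SAP*

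**What the plan says.** Four parts of the combined protocol and SAP bear on this.

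- **Exclusion criterion 3** (Study Design) excludes "Women who are pregnant (positive result for serum pregnancy test at screening visit". Pregnancy status is thus ascertained at screening, by a serum test.
- **Study Visit 1** (Study Design) schedules the test: "female participants will have a urine sampled tested to determine pregnancy status". The visit takes place "at least 1 day prior to study visit 2". The Methods paragraph of the Protocol section gives the same one-sided interval for the training done at that visit: "At least 1 day prior to study subjects will be trained to rate pain".
- **Study Visit 2** goes from fasting arrival to the catheter and fluids, then the sensory baselines ("After obtaining baseline measures (random presentation of 5 sec heat stimuli between 39 and 50°C, 5 minute presentation of a 45°C stimulus", plus the vibration threshold), then oxytocin. A blood sample is drawn before the infusion. Safety and Monitoring adds vital signs: "Peripheral oxyhemoglobin saturation, BP and HR will be measured non-invasively before and 15, 30, 60, 120, 180, 240, minutes after intravenous oxytocin injection".
- **Inclusion criterion 4** (Study Design) says that women of child-bearing potential, and those less than a year past menopause, "must be practicing highly effective methods of birth control such as hormonal methods". It also accepts double barrier methods or abstinence. It counts back at least one full cycle from dosing.

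The Risks section states what is at stake: "Risks of oxytocin are primarily restricted to uterine contraction in the presence of pregnancy".

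**The concern.** The protocol's description of oxytocin as low risk depends largely on subjects not being pregnant when they receive it. The Data Safety Monitoring Plan proposes no safety evaluation beyond what the IRB requires. Yet the one step that can detect a pregnancy is tied to the screening visit, not to the infusion, and the time between them is open-ended. A site could follow every written step and still dose a woman whose pregnancy began after her negative test. The concern is about safety and about when eligibility is verified. It does not bear on how the concentration data are analysed.

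**Working it through.** There is no planned figure to reproduce. The sample is a convenience sample of 10, and the point is procedural. The check sets the relevant text side by side.

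1. **How many tests, and when?** One is scheduled, at Visit 1. Exclusion 3 refers to a screening visit. Only two visits are described and consent is signed at the first, so the screening visit can only be Visit 1. Exclusion 3 says serum and the Visit 1 text says urine. That mismatch needs reconciling, but on either reading the test falls at Visit 1, so it does not change the timing point.

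2. **How long may the gap to dosing be?** The Methods paragraph and Study Visit 1 both give a minimum of 1 day. Neither they nor any other section gives a maximum.

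3. **What is checked at Visit 2 before oxytocin?** The listed steps are fasting arrival, catheter and fluids, heat and vibration baselines, a pre-infusion blood sample, and saturation, blood pressure and heart rate. None is a pregnancy test, a contraceptive history or an eligibility re-check.

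4. **What other safeguard exists?** Inclusion 4. Two cases show what it does and does not cover:
   - A woman who stops contraception shortly before dosing breaches the criterion on paper, but no Visit 2 step would reveal it.
   - A woman whose contraception fails after Visit 1 has complied throughout, and no step would reveal the pregnancy.

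5. **How many women?** Equal numbers of men and women are planned: 10 / 2 = 5 women. If all 12 permitted subjects are studied and the sexes stay balanced, 12 / 2 = 6. This is a ceiling. Enrolment runs to age 60, and women who are not of child-bearing potential are not at risk.

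6. **How long could the gap be in practice?** The version date is 6/11/2019 (read as 11 June), and the Background says the data are for a September 2019 grant application. If that application bounds the study, which is an assumption, 11 June to 1 September is 19 + 31 + 31 + 1 = 82 days. To 30 September it is 82 + 29 = 111 days. The longest gap would then be about 12 to 16 weeks (82 / 7 = 11.7; 111 / 7 = 15.9). This is an outer limit, not an estimate of usual practice.

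7. **Can a probability be given?** No. The documents contain no conception rate, no contraceptive failure rate and no expected interval between visits.

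**The case against.** The strongest reply is that contraception is already required and is tied to dosing, so the Visit 1 test is not the only protection. That is correct. A reader might infer that nothing else stands between a pregnant woman and the infusion, and inclusion 4 rules that reading out. What stands is narrower: contraception reduces the chance of pregnancy but does not detect one, and the protocol itself asks for a test as well.

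A reader might also infer that exclusion 3 would admit a woman known to be pregnant on the dosing day, because it mentions only the screening result. The text does not support this. The criterion opens by excluding pregnant women, and the parenthesis is reasonably read as the means of finding out. The gap is in verification, not in intent.

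The visits may well be close together. The grant timetable is short, and Visit 1 exists partly to train subjects for later testing, which works against long delays. Long gaps are therefore not shown to be expected. They are also not prevented.

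Three further inferences should be resisted:

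- That any gap longer than a menstrual cycle includes an ovulation the test does not cover. Hormonal contraception is the first method the criterion names, so this cannot be assumed for every woman.
- That a missed pregnancy would distort the pharmacokinetic results. Such a woman would fall outside the non-pregnant population of interest, but nothing in the documents shows that a pregnancy begun between visits would alter the concentrations.
- That all 5 or 6 women are at risk. That number is only the maximum.

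Finally, the consent pages are not available for this review and may address pregnancy between visits. The Visit 2 procedure as written would still contain no check.

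**Conclusion.** The point holds as a gap in verification. Pregnancy status is tested once, at Visit 1. The interval to dosing has a floor of 1 day and no ceiling, and nothing at Visit 2 re-checks status or contraception before oxytocin. An undetected pregnancy from contraceptive failure or undisclosed non-adherence after Visit 1 is therefore possible under full compliance with the written procedures. It concerns the risk that the protocol ranks first for this drug.

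The size is bounded at about 5 to 6 women, probably fewer. The likelihood for any one of them cannot be computed from the documents, and inclusion 4 makes it lower than it would otherwise be. The conclusion rests on two assumptions: that the screening visit is Visit 1, and that the Visit 2 description lists all the steps before dosing. This is an inexpensive improvement that should be made. It is not a flaw that undermines the study.

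**What to change.** - **Study Visit 2:** add a pregnancy test on the morning of the visit for women covered by inclusion 4, with the result known before the infusion starts. This can repeat the Visit 1 test or replace it.
- **Exclusion 3 and Study Visit 1:** reconcile both with that step, so that all three places agree on when the test is done and whether it uses serum or urine.
- **Optional:** state a maximum interval between the visits, after which eligibility is re-checked.

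The cost is a short amendment and, if the test is repeated rather than moved, one extra point-of-care test with a few minutes' work for each of at most about 6 women. Baseline testing already precedes the infusion, so no extra visit or staff is needed.

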## **Study Visit 2**

On the second visit, the participant will report to the CRU, in the morning after having had nothing to eat or drink since midnight. A peripheral intravenous catheter will be inserted into a vein in an upper extremity and lactated Ringers solution infused at 1.5 ml/kg/hr for the duration of the study. After obtaining baseline measures (random presentation of 5 sec heat stimuli between 39 and 50°C, 5 minute presentation of a 45°C stimulus, and vibration frequency perception threshold as described in Visit 1), oxytocin (Pitocin®, 10 IU) will be administered intravenously over 10 minutes.

Venous blood will be sampled (5 ml) before the infusion and at 2, 5, 10, 15, 30, 45, 60, 90, 120, 180, and 240 minutes after oxytocin injection via the indwelling intravenous catheter. We will also repeat vibration frequency perception threshold in fingertips and wrist between the samples after samples at 5, 20, 45, 60, 120, and 180 minutes. In addition, we will ask them to rate pain intensity every minute for 5 minutes with a 45° stimulus after samples at 30, 60, 120, and 180 minutes (adjacent figure) and rate pain intensity to single, 5 second duration stimuli from 39°C to 50°C after samples at 60, 120, and 180 minutes as on the first visit.

